# 1.1.2 Secondary Objectives

The secondary study objective is to assess the long term safety of multiple treatments of Dysport used in this study population.

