## 1.2 Study Design

This is a phase III, multicentre, double blind, prospective, randomised, controlled multiple treatment study. Subjects will receive a maximum of four treatments over the course of a minimum of one year's study participation.

At study entry, subjects will be randomised into one of the following three treatment groups for Treatment Cycle 1:

- Group A: Dysport 16 U/kg in one upper extremity (the study limb).
- Group B: Dysport 8 U/kg in the study limb.
- Group C: Dysport 2 U/kg in the study limb.

Randomisation will be in a 1:1:1 ratio. Stratification will be performed according to age range (2 to 9 years and 10 to 17 years) and BTX (Botulinum Toxin) naïve or non-naïve status assessed at baseline.

For Treatment Cycles 2, 3 and 4, subjects are planned to receive Dysport 8 U/kg or 16 U/kg according to the treatment allocation by the IRS and will remain double blind throughout the study. However, it is possible that subjects will not receive the planned treatment as dose adaptations (reduction or increase) will be possible based upon the Investigator's judgements regarding safety and efficacy. The total dose for the study limb must not exceed 320 U in the 8 U/kg group and 640 U in the 16 U/kg group.

The planned retreatment interval is 16 weeks and a maximum of four treatments will be administered.

At study entry, a primary targeted muscle group (PTMG), either the elbow flexors or wrist flexors, will be nominated by the Investigator. The PTMG can be changed for subsequent treatments, from elbow to wrist flexors or wrist to elbow flexors, provided that the following criteria are fulfilled:

- The Modified Ashworth Scale (MAS) score of the other muscle group not selected for the last treatment (new PTMG) must be higher than the last treatment PTMG, and
- The new PTMG must have a modified MAS score of greater or equal to 1+.

For Treatment Cycles 2, 3 and 4, injection into the lower extremity/extremities and the nonstudy upper limb will be allowed at the same time as the study limb is injected.

The stages of the study and the planned doses for the study are provided in Figure 1.

Figure 1 Planned Study Structure and Dose Modifications Available During the Study

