#### 1.2.1 Study Treatment

Subjects will receive a fixed dose of Dysport 2 U/kg, 8 U/kg or 16 U/kg in the study upper limb in Treatment Cycle 1 and are planned to receive Dysport 8 U/kg or 16 U/kg in subsequent treatments according to the treatment allocation by the IRS, illustrated below, and both Investigators and subjects will remain blinded throughout the study. The allocated dose will be reconstituted to a fixed volume of 1.6 mL for injection.

| Group            | Number of | Treatment              | Treatment Cycles                 |
|------------------|-----------|------------------------|----------------------------------|
|                  | Subjects  | Cycle 1 (a) | 2, 3 and 4 (a) |
| А                | 70        | Dysport 16 U/kg        | Dysport 16 U/kg                  |
| В                | 70        | Dysport 8 U/kg         | Dysport 8 U/kg                   |
| C (b) | 70        | Dysport 2 U/kg         | Dysport 8 U/kg or                |
|                  |           |                        | Dysport 16 U/kg                  |

 Table 1
 Planned Dysport Dose per Group and Treatment Cycle

 $^{(a)}$  The total dose for the study limb must not exceed 320 U in the 8 U/kg group and 640 U in the 16 U/kg group.

(b) In this group, dynamic dose dispensing will be done by IRS at Treatment Cycle 2 to maintain a balance between subjects receiving 8 U/kg and 16 U/kg.

For Treatment Cycles 2, 3 and 4, and according to subject response, if any given total dose is not tolerated, the Investigator will request a dose reduction of 50% in the IRS. CC

For Treatment Cycles 3 and 4, if any given total dose is not adequate for the treatment of the subject's upper limb spasticity, the Investigator can request a dose increase in the IRS.

dose increase is possible for those subjects who were given Dysport 16 U/kg as the subject was already given the highest dose allowed in the study. CCI

No

CCI

. If there is no need to inject the lower limbs, and only the non-study upper limb is to be injected (on top of the study upper limb), the dose in the non-study upper limb should not exceed the dose detailed in Table 3.

 Table 3
 Dysport Dose in the Non-Study Upper Limb at Treatment Cycles 2, 3, and 4

| Body Weight (kg) | Maximum Dose                   |
|------------------|--------------------------------|
| 10 to 40         | 5 U/kg, calculated up to 40 kg |

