## Sample Size of the Study

Given the above sample size estimates, a targeted study sample size of 210 randomised subjects (i.e. 70 randomised subjects per treatment group) is considered sufficient to meet both the primary efficacy objective and the long term safety objectives.

Using a sample size of 210 as the largest of the three required figures means the actual power for the testing on the primary efficacy endpoint and the testing on the first secondary efficacy endpoint rises to 99% and 99%, respectively. As a result, the actual power of the study to detect a significant effect of any tested Dysport dose for both efficacy endpoints (US-targeted methodology) is 98% (= 99% x 99%).

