- Any TEAE leading to withdrawal (TEAEWD)
- Any TEAE leading to death
- Any SAEs

In the above table, intensity, causality and causality combined with intensity of TEAEs, subjects will be presented in all the categories of intensity and causality in which their TEAE(s) have been reported.

Presentation by study limb dose will also include overall summary of all AEs for all treatment cycles combined.

In addition to the above, the following TEAE summary tables will be presented by treatment group for **study limb dose** across all treatment cycles (using the dose groups specified in Section 3.2.1.2 as administered in the specified Treatment Cycle):

- TEAEs with the number and percentage of subjects and the number of occurrences presented by primary SOC and PT
- TEAEs by intensity with the number and percentage of subjects and the number of occurrences by primary SOC and PT
- TEAEs by causality with the number and percentage of subjects and the number of occurrences by primary SOC and PT
- TEAEs by causality combined with intensity with the number and percentage of subjects and the number of occurrences by primary SOC and PT

- SAEs with the number and percentage of subjects with SAEs and the number of occurrences by primary SOC and PT
- SAEs by intensity with the number and percentage of subjects and the number of occurrences by primary SOC and PT
- SAEs by causality with the number and percentage of subjects and the number of occurrences by primary SOC and PT
- SAEs by causality combined with intensity with the number and percentage of subjects and the number of occurrences by primary SOC and PT
- TEAEWDs with the number and percentage of subjects with TEAEWDs and the number of occurences by primary SOC and PT
- TEAEWDs by intensity with the number and percentage of subjects and the number of occurrences by primary SOC and PT
- TEAEWDs by causality with the number and percentage of subjects and the number of occurrences by primary SOC and PT
- TEAEWDs by causality combined with intensity with the number and percentage of subjects and the number of occurrences by primary SOC and PT
- Non serious TEAEs by treatment group, with the number and percentage of subjects with non serious TEAEs and the number of occurrences presented by primary SOC and PT, for all non serious TEAEs occurring for  $\geq 5\%$  of subjects in at least one treatment group at the PT level

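### The adverse event summaries pooled over all cycles set crude percentages side by side in dose columns with very unequal planned exposure, and no rate per cycle or per unit of time is planned

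*SAP*

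**What the plan says.** The secondary objective (SAP 1.1.2) concerns repeated dosing: "The secondary study objective is to assess the long term safety of multiple treatments of Dysport used in this study population".

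After Cycle 1, subjects "are planned to receive Dysport 8 U/kg or 16 U/kg in subsequent treatments according to the treatment allocation by the IRS" (SAP 1.2.1), so 2 U/kg is planned only for Group C in Cycle 1. Group C is then divided: "dynamic dose dispensing will be done by IRS at Treatment Cycle 2 to maintain a balance between subjects receiving 8 U/kg and 16 U/kg". On number and spacing, "The planned retreatment interval is 16 weeks and a maximum of four treatments will be administered" (SAP 1.2).

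SAP 3.2.3.1 sets out an overall AE summary by study limb dose for Cycles 1 to 4 and adds: "Presentation by study limb dose will also include overall summary of all AEs for all treatment cycles combined". Under its heading on AEs of special interest for repeat treatment, the total body dose tables also include an AE summary over all cycles combined.

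Three rules govern how these tables fill up:
- SAP 3.2.3.1 assigns an AE to the dose received in the cycle of onset, and in the term and organ-class tables counts a subject once per category.
- SAP 3.2.15 takes subjects as the denominator of percentages.
- SAP 3.2.1.2 labels the low column for repeat treatment 2/4 U/kg, with a cut-off at 6 U/kg.

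The readable text plans no AE rate per cycle or per unit of subject time.

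**The concern.** A subject treated four times has four chances to enter the numerator of a crude percentage; a subject treated once has one. If the columns of a pooled table differ in cycles per subject, their percentages differ even when the risk of each treatment is identical. Here the imbalance follows the dose, because the low dose is planned for a single cycle. It would therefore look like a dose gradient.

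The pooled summary is an obvious place to look for a quick reading of safety over the whole study, and nothing in the SAP warns against reading across its columns. A true dose pattern could be exaggerated, or one suggested where none exists, in a paediatric safety table.

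**Working it through.** **Figures in the documents.** They give no AE rate and no mean number of cycles by dose column, so there is no stated figure to reproduce. The group sizes agree: "70 randomised subjects per treatment group" and "Randomisation will be in a 1:1:1 ratio" give 3 × 70 = 210.

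**Inputs.**
- 70 subjects per group; at most four cycles, planned 16 weeks apart (SAP 1.2 and sample size section).
- Group A has 16 U/kg and Group B 8 U/kg in all cycles; Group C has 2 U/kg in Cycle 1, then 8 or 16 U/kg in up to three cycles (SAP 1.2.1, Table 1).
- Assumption: Group C splits 35/35.

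**Planned exposure per column.**
- Low column: 70 × 1 = 70 cycles in 70 subjects, or 1.00 per subject (16 weeks).
- 8 U/kg, and likewise 16 U/kg: 70 × 4 + 35 × 3 = 385 cycles in 105 subjects, or 3.67 per subject (3.67 × 16 = 58.7 weeks).

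**Effect on crude percentages.** Assume the same AE probability p per cycle at every dose, independent cycles, full retention and no dose changes. The low column shows p. Each higher-dose column shows

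(2/3)[1 − (1 − p)^4] + (1/3)[1 − (1 − p)^3].

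| p per cycle | Low column | 8 or 16 U/kg column |
|---|---|---|
| 5% | 5% | 17.1% |
| 10% | 10% | (2/3)(0.3439) + (1/3)(0.271) = 32.0% |
| 20% | 20% | (2/3)(0.5904) + (1/3)(0.488) = 55.6% |
| 30% | 30% | (2/3)(0.7599) + (1/3)(0.657) = 72.6% |

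**How far 3.67 could move.** It is a planned maximum. Each assumption is varied alone:
- Group C split 40/30 or 30/40: 3.64 to 3.70.
- Retention of 95%, 90% or 80% per cycle: 3.43, 3.21 or 2.81.
- Nobody goes beyond three or two treatments: 2.67 or 1.67.
- 25% of 8 U/kg subjects raised to 16 U/kg at Cycle 3: 3.17 (8 U/kg) and 3.33 (16 U/kg).
- 10% or 25% of 8 U/kg subjects reduced to 4 U/kg: the low column rises to 1.22 or 1.45 cycles per subject.

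In every case the higher-dose columns keep more cycles per subject than the low column.

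**Dropout.** Take p = 10% and 80% retention per cycle. In Group B, the chance of no AE is 0.2(0.9) + 0.16(0.81) + 0.128(0.729) + 0.512(0.6561) = 0.739, so 26.1% have one. In the 28 Group C subjects who reach 8 U/kg, it is 0.2(0.9) + 0.16(0.81) + 0.64(0.729) = 0.776, so 22.4% have one. Weighted: (70 × 26.1% + 28 × 22.4%)/98 ≈ 25%, against 10% in the low column.

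**Correlation within a child.** Take p = 20% and a beta-binomial model with an assumed within-child correlation of 0.3. The chance of no AE is 0.614 over three cycles and 0.560 over four. The higher-dose column shows (2/3)(0.440) + (1/3)(0.386) ≈ 42%, rather than 56%, still against 20%.

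**With a cycle denominator.** At p = 10%, the expected cycles with an AE are 7 of 70 in the low column and 38.5 of 385 in each higher-dose column. Both are 10 per 100 cycles.

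For the total body dose table the low column is at most 5 U/kg. Injection of other limbs is discretionary, so the documents do not allow a planned number of cycles per column there.

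**The case against.** The strongest answer is that the SAP does not rest its safety comparison on this table. Section 3.1 places the comparison with 2 U/kg in Cycle 1, which is randomised with 70 per group and one cycle each; extra exact-dose tables support it. Sections 2.6 and 3.1 evaluate repeat-treatment safety cycle by cycle, and 3.1 puts the focus on 8 and 16 U/kg, whose planned exposure is equal (385 cycles in 105 subjects each). All of this stands. A reader might infer that the trial's safety comparison between doses is confounded, or that the pooled table is the designated long-term summary and the by-cycle tables cannot make up for it. The documents support neither inference.

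Two shorthand statements would also go too far. The documents do not give about 3.7 cycles as the exposure actually obtained: treatment stops after Week 52 for subjects outside the 16 to 22 week intervals, and doses may change. Nor is the low column strictly one cycle at 2 U/kg, because reduced-dose cycles enter it.

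The SAP also softens the problem. It gives numbers of occurrences in the term and organ-class tables, classifies events by time since last injection, and summarises exposure in 3.2.9. Safety is descriptive and no AE test between doses is described. None of this supplies a rate or an exposure denominator for the pooled table.

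Finally, the table templates are in a separate document and the table index is redacted. Crude subject percentages are inferred from the general rule in 3.2.15, and a footnote in the template cannot be excluded.

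**Conclusion.** The point holds for summaries pooled over cycles, and only for those. Under the general percentage rule, the all-cycles AE summary by study limb dose would compare about one planned cycle per subject in the low column with up to 3.67 at 8 or 16 U/kg. Equal risk per cycle would then look like a dose gradient: 10% against up to 32%, or 20% against up to 56%. These sizes are illustrations at the upper end. They rest on assumed risks per cycle, independent cycles, full retention and no dose changes. With correlated cycles or dropout the gap is smaller (20% against about 42%, 10% against about 25%) but remains. The total body dose summary has the same structural weakness, of unknown size. This is an inexpensive improvement to a table that could mislead, and does not call the main safety analyses into question.

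**What to change.** In both combined summaries:

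1. Show the number of treatment cycles and patient-years for each dose column.
2. Add AEs per 100 treatment cycles, with 95% confidence intervals that allow for repeated cycles within a child (for example, a robust variance clustered on subject). Optionally add AEs per 100 patient-years.
3. State the rule for splitting exposure: each cycle, and its time, belongs to the dose column of that cycle, matching the existing rule for assigning AEs.
4. Footnote that crude percentages are not comparable across dose columns because exposure differs, and refer to the Cycle 1 tables for the comparison with 2 U/kg.

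The cost is one added table block and a short paragraph in the SAP. Cycle duration and exposure are already derived (SAP 3.2.13.9 to 3.2.13.11), and cycle and dose are already attached to each AE. No new data are needed and the design does not change.

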All TEAEs will be summarised overall and by treatment group with the number and percentage of subjects with TEAEs presented by primary SOC and preferred term. If a subject experiences more than one TEAE within a category (preferred term or primary SOC), the subject will be counted only once in that category.

In addition, TEAEs will be tabulated by decreasing overall preferred term frequency, intensity, causality, and causality combined with intensity.

In the event of multiple reports of the same preferred term for a subject, the maximum intensity (severe>missing>moderate>mild) and the most serious causality (related>not related) will be counted in the summary of TEAEs by intensity and causality.

The number of occurrences of TEAEs coded with the same preferred term will also be presented by treatment group.

All TEAEs will be flagged in the AE listing.

All SAEs and AEs leading to withdrawals will be summarised overall and by treatment group with the number and percentage of subjects with SAEs and AEs leading to withdrawals presented by primary SOC and preferred term.

Vital Signs

Vital signs data will be presented in a listing which will be sorted by treatment group, subject ID, and assessment visit. Any unscheduled assessments will be flagged in the listing.

Baseline values for each treatment group will be defined as the last measurements collected prior to administration of the study treatment.

For each treatment group, descriptive statistics on raw assessments and changes from baseline at each assessed study visit will be provided.

Laboratory Parameters

For clinical laboratory safety tests (clinical chemistry including serum ALP - total and bone isoenzyme, and HbA1c), all the abnormal values will be flagged in the data listings and a list of clinically significant abnormal values will be presented by treatment group and by subject ID for evaluations at baseline and at the end of study visit or early withdrawal.

Shift tables from baseline of the number and percentage of subjects with low, normal or high values will also be presented by treatment group.

The Presence of BTX-A-Abs

The number and percentage of subjects with the presence of BTX-A-Abs (both binding and neutralising) at baseline and at the end of study visit or early withdrawal will be compared between treatment groups.

Electrocardiograms

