- TEAEs by treatment group, with the number and percentage of subjects with TEAEs and the number of occurrences presented by primary SOC and PT, for all TEAEs occurring for  $\geq 3\%$  of subjects and more than 1 subject in at least one treatment group at the PT level

If a subject experiences more than one TEAE within a category (PT or primary SOC) the subject will be counted only once in that category.

In the summary of TEAEs by intensity and causality, in the event of multiple reports of the same PT for a subject, the maximum intensity (severe>missing >moderate>mild) and the most serious causality (related>not related) will be counted.

For all AESIs the following selected tables will be produced **by study limb dose group** across all treatment cycles 1, 2, 3, and 4:

- Overall summary table of all AESIs
- AESIs with the number and percentage of subjects and the number of occurrences presented by primary SOC and PT
- AESIs by causality combined with intensity with the number and percentage of subjects and the number of occurrences by primary SOC and PT.

## TEAEs for fixed dose Treatment Cycle 1

In addition to the TEAE summary tables by study limb dose described above (including Treatment Cycle 1), the following tables will be produced by study limb dose group for those subjects who received the **exact dose in the study limb** (see Section 3.2.1.2). These tables will be provided for (TE)AEs at Treatment Cycle 1.

- Overall summary table of all AEs
- TEAEs with the number and percentage of subjects and the number of occurrences presented by primary SOC and PT

- TEAEs by intensity with the number and percentage of subjects and the number of occurrences by primary SOC and PT
- TEAEs by causality with the number and percentage of subjects and the number of occurrences by primary SOC and PT
- TEAEs by causality combined with intensity with the number and percentage of subjects and the number of occurrences by primary SOC and PT
- SAEs with the number and percentage of subjects with SAEs and the number of occurrences by primary SOC and PT
- TEAEWDs with the number and percentage of subjects with TEAEWDs and the number of occurrences by primary SOC and PT
- TEAEs by treatment group, with the number and percentage of subjects with TEAEs and the number of occurrences presented by primary SOC and PT, for all TEAEs occurring for  $\geq 3\%$  of subjects and more than 1 subject in at least one treatment group at the PT level.

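### Taking maximum intensity and worst causality separately for repeated reports of one preferred term is right for the one-way tables. If carried into the causality-by-intensity tables, it can show a child as 'related and severe' when no such event was reported.

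*SAP*

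**What the plan says.** SAP 3.2.3.1 (Adverse Events) contains three statements that bear on this point.

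- **The rule for repeats of one PT.** Its scope is: "In the summary of TEAEs by intensity and causality, in the event of multiple reports of the same PT for a subject". Its content is that the highest intensity (severe first, then missing, moderate, mild) "and the most serious causality (related>not related) will be counted". Protocol 11.4.4 has the same rule: "the maximum intensity (severe>missing>moderate>mild) and the most serious causality (related>not related) will be counted in the summary of TEAEs by intensity and causality". Neither document says that the two values must come from the same report.
- **The once-only rule.** "If a subject experiences more than one TEAE within a category (PT or primary SOC) the subject will be counted only once in that category". It does not say which report represents the child.
- **The rule for the overall adverse event summary.** There, "subjects will be presented in all the categories of intensity and causality in which their TEAE(s) have been reported". The sentence is tied to the table just above it, so it covers the overall summary only.

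The SAP then lists cross-classified tables by PT within system organ class (SOC), including this one: "TEAEs by causality combined with intensity with the number and percentage of subjects and the number of occurrences by primary SOC and PT". The study-limb-dose list has matching tables for serious events and for events leading to withdrawal. Events of special interest (AESIs) have their own: "AESIs by causality combined with intensity with the number and percentage of subjects and the number of occurrences by primary SOC and PT".

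The overall summary has an unknown/missing causality category, and SAP 3.2.4.1 (Safety) keeps missing causality as a category of its own. The causality order in the repeat rule ranks only related and not related.

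**The concern.** A cell in a cross-classified table should describe something that was reported. Two maxima taken on separate axes can come from two different reports, and the resulting pair may then match neither. 'Related and severe' is the cell a reader looks to first for harm attributed to the drug, and long-term safety of multiple treatments is the secondary objective.

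The plan expects the situation that triggers this. SAP 3.2.3.1 provides for events whose intensity changes in another cycle, and SAP 3.2.13.6 provides for several episodes of the same event.

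The outputs could also disagree with one another. The overall summary, which shows reported categories, could print 0 children as related and severe while the PT table prints 1. The PT tables also give numbers of occurrences, so a row could show 1 child and 0 occurrences. For AESIs, and for the Cycle 2 to 4 tables split by whether other limbs were injected, the combined table is listed without separate intensity and causality tables beside it, so the artefact would be harder to notice.

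**Working it through.** The plan states no figure to reproduce, because this is a counting rule. The check is to list the possible report patterns and apply the rule to each.

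**Inputs.** Causality: related or not related, in the SAP's order. Intensity: severe > missing > moderate > mild, in the SAP's order. That gives 2 × 4 = 8 kinds of report.

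**Rule as written.** Assigned cell = (worst causality over the reports, highest intensity over the reports). A cell is contrived if no report in the set has that pair.

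**Two reports of one PT.** There are 8 × 9 / 2 = 36 unordered sets. Six give a contrived cell:

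| Not related report | Related report | Cell assigned |
|---|---|---|
| moderate | mild | related, moderate |
| missing | mild | related, missing |
| missing | moderate | related, missing |
| severe | mild | related, severe |
| severe | moderate | related, severe |
| severe | missing | related, severe |

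Three of the six land in 'related and severe'. Without the missing level, 3 of 21 sets are contrived and 2 of those are 'related and severe'.

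**Three reports.** There are 8 × 9 × 10 / 6 = 120 sets; 30 are contrived, 18 of them as 'related and severe'. These are counts of possible patterns, not expected frequencies.

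**Direction.** A child with a genuine related and severe report has both maxima at the top and is always counted there. The rule can therefore add children to that cell but never remove one.

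**Size of one case.** Planned Cycle 1 columns hold 70 children: 1/70 = 1.4%, against 0%. From Cycle 2, with an even split of Group C, no dropout and no dose changes, a planned 8 or 16 U/kg column holds about 70 + 35 = 105, and 1/105 = 1.0%.

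**Missing causality.** A PT reported once with missing causality and once as not related has no defined place in the causality-only table, because missing is not in the order.

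**The case against.** The strongest reply concerns scope. The documents use three labels: by intensity, by causality, and by causality combined with intensity. The repeat rule names a summary by intensity and causality, which can mean just the two one-way tables, where separate maxima are correct. Protocol 11.4.4 also says that in summaries of intensity, causality and the two combined, a subject may fall in more than one category.

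This stands in part. The rule is not expressly assigned to the combined tables, and a reader who infers that the SAP mandates the artefact goes too far. But on the narrow reading the combined PT tables have no selection rule at all. The Protocol's multi-category sentence directly follows its mention of the overall summary and probably covers only that table. The Protocol's repeat rule comes straight after a sentence that lists the combined tabulation. A programmer could reasonably apply it there.

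Two stronger inferences are tempting:

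- **That the error grows with the number of cycles and is worst at 8 and 16 U/kg.** The documents do not show this. SAP 2.6 and 3.2.1.2 set repeat-treatment safety by cycle and by the dose received in that cycle, and 3.2.3.1 assigns each event to its cycle. Many tables would therefore pool repeats only within one cycle.
- **That the cell is overstated by some multiple.** With reports assumed independent, 2–10% severe and 10–30% related, the ratio is 1.6 to 2.7 for a child with two or three reports of one PT. No document gives any of those rates, the frequency of repeats, or support for independence. It is not an expected error for a column.

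Three further points stand. The overall summary is unaffected, and all events are listed. The Protocol asks that withdrawal be attributed to a single episode, and AESIs with another explanation are excluded, so mixed sets should be less common in those tables. Table templates are in a separate document, where a footnote might settle the matter; nothing in the text reviewed does.

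**Conclusion.** The point holds as a gap in the counting rule. Separate maxima are correct for the one-way tables. If used in the combined SOC/PT tables, they can print a causality-intensity pair that no report had, including 'related and severe'. For that cell the error is only upward.

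How often it would happen cannot be derived from the documents. It requires at least two reports of the same PT in one child, with differing causality and intensity, within the period the table covers. The 1.4% is the effect of one such child in a planned Cycle 1 column, not a forecast. No hypothesis test and no entry in the overall adverse event summary is affected. The unranked missing causality category is a smaller gap in the same sentence. Both should be settled before unblinding.

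**What to change.** In SAP 3.2.3.1:

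1. State that the separate maxima apply only to the tables by intensity alone and by causality alone.
2. For every SOC/PT table of causality combined with intensity, extend the rule already used for the overall summary: the child appears once in each causality-intensity pair actually reported for that PT. Keep the once-only count for the PT and SOC totals. Add a footnote that the categories are not mutually exclusive.
3. Give missing causality a place in the order used for the causality-only table.

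The cost is a few sentences, a footnote and a small programming change, with no new data. The drawback is that rows in a combined table may sum to more than the number of children with that PT.

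An alternative is to count one actual report per child, chosen by causality first and then intensity. It also removes every contrived cell (0 of 36 two-report sets and 0 of 120 three-report sets). However, a child with a severe unrelated and a mild related report would appear only as related and mild, and the severe report would drop out of the combined subject count. Showing every reported pair avoids that.
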